7.2.3. Subgroup Analyses for the Primary Endpoint

Subgroup analysis will be performed based on the following participant-demographic and baseline disease-characteristic variables for those participants whose data are available:

- Baseline IGA score (2, 3)
- Baseline EASI score (≤ 7 , > 7)
- Age (2 to 6 years, 7 to < 12 years)
- Sex (male, female)
- Race
- Country (United States or Canada)
- Prior TCS therapy (yes/no)
- Prior TCI therapy (yes/no)
- Prior systemic therapy (yes/no)
- Prior AD therapy (yes/no)

7.2.4. Sensitivity and Supportive Analyses for the Primary Endpoint

7.2.4.1. Longitudinal Logistic Regression With Repeated Measures

To adjust for the dependence underlying the hierarchical multilevel data structure (visit, participant, and site), a longitudinal logistic regression with repeated measures will be applied. The 3 level structures in the model are

- Level 1: visit
- Level 2: participant
- Level 3: site,

where visits are nested within participants and participants are further nested within sites.

The binary response (IGA-TS) of each participant at Weeks 2, 4, and 8 will be included as the dependent variable. Treatment (1.5% BID, 0.75% BID, and vehicle BID), randomization stratification factors (baseline IGA score and age), visit, and treatment-by-visit interaction will

be included as fixed effects. Site level intercept and participant nested in site level intercept will be included as random effects. The within-participant and within-site errors will be modeled by an unstructured variance-covariance matrix. The Kenward-Roger approximation will be used to estimate denominator degrees of freedom for this model.

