1. PROTOCOL SUMMARY

Protocol Title:

Topical **Ruxolitinib** Evaluation in **Atopic Dermatitis** Study **3** (TRuE-AD3)

A Phase 3, Double-Blind, Randomized, Vehicle-Controlled, Efficacy and Safety Study of Ruxolitinib Cream Followed by a Long-Term Safety Extension Period in Children (Ages \geq 2 Years to < 12 Years) With Atopic Dermatitis

Protocol Number: INCB 18424-305

Objectives and Endpoints:

[Table 1](#) presents the primary and key secondary objectives and endpoints.

Table 1: Primary and Key Secondary Objectives and Endpoints

Objectives	Endpoints
Primary	
To establish the efficacy of ruxolitinib cream in participants with AD.	Proportion of participants who achieve IGA-TS at Week 8.
Key Secondary	
To further assess the treatment effects of ruxolitinib cream.	Proportion of participants with a \geq 4-point improvement in Itch NRS score from baseline to Week 8. Proportion of participants with a \geq 4-point improvement in Itch NRS score from baseline to Day 7 (Week 1). Proportion of participants with a \geq 4-point improvement in Itch NRS score from baseline to Day 3.

Overall Design:

[Table 2](#) presents the key study design elements. Further study details are presented after the table.

Table 2: Key Study Design Elements

Study Phase	Phase 3
Clinical Indication	Atopic dermatitis
Population	Children aged \geq 2 years to $<$ 12 years (with at least 40% of participants ages \geq 2 years to 6 years) who have been diagnosed with AD for at least 3 months, have an IGA score of 2 to 3, and have %BSA involvement (excluding the scalp) of 3% to 20%.
Number of Participants	Approximately 315 participants will be randomized 2:2:1 to 1 of 3 treatment groups (ruxolitinib cream 0.75% BID [n = 126], ruxolitinib cream 1.5% BID [n = 126], or vehicle cream BID [n = 63]). The study will be conducted at approximately 60 sites in the United States and Canada.
Study Design	Randomized (2:2:1), double-blind, VC period (8 weeks) followed by an LTS period (44 weeks) and a 30-day safety follow-up period after the last application of study cream. In the LTS period, participants initially randomized to vehicle cream will be rerandomized (1:1) in a blinded manner to ruxolitinib cream 0.75% or 1.5%, and participants initially randomized to an active treatment group will continue in the same treatment group.

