10.4.1. Primary Analysis

The primary analysis will be based on the ITT population. The primary alternative hypothesis (superiority of each active ruxolitinib arm, 1.5% BID or 0.75% BID, compared with vehicle) will be tested at a 2-sided $\alpha = 0.025$ level using logistic regression. This model will include the treatment group (1.5% BID, 0.75% BID, and vehicle) and stratification factors (baseline IGA score and age). Exact logistic regression ([Mehta and Patel 1995](#)) will be used for all of the comparisons if any of the treatment strengths have an expected cell count < 5 .

The difference in IGA-TS rates (ruxolitinib cream/vehicle) at Week 8 will be computed. The 95% confidence interval for the difference will be computed based on a large-sample normal approximation with continuity correction. All nonresponders during the VC period, as well as all participants who discontinue study treatment at any time before the timepoint of interest, or discontinue from the study for any reason, will be defined as nonresponders for the nonresponder imputation analysis. Subgroup analysis by baseline characteristic (eg, IGA score, country, and age) will be performed. Details will be provided in the SAP. The following approaches may be performed for sensitivity analyses:

- Longitudinal logistic regression with repeated measures:

To adjust for the dependence underlying the hierarchical multilevel data structure (visit, participant, and site), a longitudinal logistic regression with repeated measures will be applied. In the model, visits are nested within participants, which are further nested within sites.

The primary endpoint binary response of each participant at Week 2, Week 4, and Week 8 will be included as the dependent variable. Treatment (1.5% BID, 0.75% BID, and vehicle BID), the randomization stratification factors (baseline IGA score and age), visit, and treatment by visit interaction will be included as fixed effects. Site level intercept and participant nested in site level intercept will be included as random effects. The within-participant and within-site errors will be modeled by an unstructured variance-covariance matrix. The Kenward-Roger approximation will be used to estimate denominator degrees of freedom for this model.

- Multiple imputation:

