1. INTRODUCTION

Study INCB 18424-305 is a randomized, double-blind, vehicle-controlled study with an LTS period in pediatric participants aged ≥ 2 to < 12 years with AD eligible for topical therapy. This Phase 3 study will be conducted at roughly 60 sites in the United States and Canada. Approximately 315 participants will be randomized 2:2:1 to blinded treatment with either ruxolitinib 1.5% cream BID, ruxolitinib 0.75% cream BID, or vehicle cream BID; stratification will be by baseline IGA score and age. Enrollment will be capped such that no more than approximately 25% of randomized participants have a baseline IGA score of 2. At least 40% of the overall study population will consist of children aged ≥ 2 to 6 years. In this trial, participants will apply blinded study treatment for 8 weeks followed by a randomized 44-week LTS extension period. In the LTS period, participants initially randomized to vehicle cream will apply either ruxolitinib 0.75% or 1.5% cream BID; this will replicate the design of the earlier pivotal studies (INCB 18424-303 and INCB 18424-304) in adolescents and adults with AD.

The purpose of this SAP is to provide details of the statistical analyses that have been outlined in the INCB 18424-305 Protocol. The Department of Biostatistics or designee will execute the scope of this plan [REDACTED]
[REDACTED].

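### The longitudinal logistic sensitivity model is over-parameterised and ambiguous: the participant intercept overlaps with the unstructured visit matrix, and an unstructured within-site error matrix is undefined

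*SAP*

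**What the plan says.** The two documents describe the same model. SAP 7.2.4.1 defines the outcome: "The binary response (IGA-TS) of each participant at Weeks 2, 4, and 8 will be included as the dependent variable". The fixed effects are treatment, the two stratification factors, visit and treatment by visit. The hierarchy has three levels, "where visits are nested within participants and participants are further nested within sites".

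For the random effects, Protocol 10.4.1 states: "Site level intercept and participant nested in site level intercept will be included as random effects". The SAP says the same. In both documents a separate sentence follows: "The within-participant and within-site errors will be modeled by an unstructured variance-covariance matrix". The last element is: "The Kenward-Roger approximation will be used to estimate denominator degrees of freedom for this model".

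The protocol introduces its list of sensitivity analyses with "The following approaches may be performed for sensitivity analyses", whereas the SAP says that this model will be applied. The SAP prints code for its two multiple imputations (7.2.4.2 and 7.3.2). For this model it gives no code, no estimation method and no rule for non-convergence.

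**The concern.** A participant random intercept and an unstructured residual matrix across a child's visits are two ways of representing one thing, the correlation among that child's three responses. A model normally uses one of them. Using both invites an unstable fit, or a fit in which one of the two drops out. At site level, an unstructured residual matrix needs rows that mean the same thing in every site, and children do not supply such rows.

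At stake is the prespecified status of one robustness check. The sponsor is unblinded after the primary database lock (Protocol 10.5, SAP 10). If the model were first found to fail at that point, a replacement would have to be chosen with the treatment codes available and no written rule to follow.

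**Working it through.** The plan states no figure for this model, so there is none to reproduce. The sample-size claim (SAP 3.3, power above 95%) does not depend on it. As a side check, Fisher exact power for 126 versus 63 at two-sided 0.025 is 99.9% for 51% versus 14% and 99.5% for 47% versus 14%, in agreement with the plan.

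**Inputs.** Three visits per child (SAP 7.2.4.1); 315 participants, 126/126/63 (Protocol 1); about 60 sites (SAP 1); planning rates 51%, 47% and 14% (SAP 3.3).

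**1. Participant level, parameter count.** A 3x3 covariance block has 3 x 4 / 2 = 6 distinct elements. The literal model has 6 parameters in the unstructured matrix R plus 1 intercept variance s, which makes 7.

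**2. Gaussian-type errors.** The block is V = s·J + R, where J is the matrix of ones. Replacing s by s + c and R by R − c·J leaves V unchanged. The rank is 6 of 7, so s is fully redundant.

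**3. Binary errors, linearised.** The block is V = s·J + D·R·D, with D = diag(1/√(μ(1−μ))). Absorbing a change c in s now requires R − c·d·dᵀ, where d has elements √(μ(1−μ)). These differ between children. With the planning rates as Week 8 means, μ(1−μ) is 0.14 x 0.86 = 0.120 on vehicle, 0.51 x 0.49 = 0.250 on 1.5% and 0.47 x 0.53 = 0.249 on 0.75%. No single R absorbs the change for every child, so the rank is 7 of 7. The redundancy is near, not exact. From the expected information, the standard error of s is 2.1 to 2.8 times larger than without the residual covariances, and its estimate correlates −0.79 to −0.92 with them.

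**4. Simulated fits.** Eleven trials were simulated with 315 children, 60 sites and 3 visits. The assumed site SD was 0.4 and the participant SD 1.5 (variance 2.25). They were fitted by restricted pseudo-likelihood in purpose-written code, not SAS and without Kenward-Roger.

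| Model | Converged | Result |
|---|---|---|
| A: site and participant intercepts only | 10 of 11 | participant variance 0.54 to 1.31 where converged |
| B: A plus unstructured 3x3 residual | 7 of 11 | participant variance 0.0009 to 0.0014, at or near the lower bound |
| C: site intercept plus unstructured 3x3 residual | 10 of 11 | no participant variance by design |

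Of the four trials in which B diverged, A and C both converged in three, and neither did in the fourth. In the seven trials that B completed, its Week 8 log odds ratio for 1.5% versus vehicle matched C to within 0.002. B was then in effect model C.

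**5. The two coherent readings compared.** In the ten trials where A and C both converged, A's log odds ratio exceeded C's by 0.018 (2.172 versus 2.154) to 0.127 (2.856 versus 2.729). Standard errors were 0.377 to 0.649. The readings give different numbers, but the gaps are small beside the standard errors.

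**6. Site level, read as residuals.** The average is 315 / 60 = 5.25 children per site. Five children x 3 visits = 15 rows, with 15 x 16 / 2 = 120 elements. Six children = 18 rows, with 18 x 19 / 2 = 171 elements. The dimension changes from site to site, and no rule says which child occupies which row, so there is no common matrix to estimate.

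**The case against.** A reader might go further and infer that the model cannot be fitted, is not identified, or will not converge. The documents do not support that. The count of 7 parameters for 6 quantities settles the matter for Gaussian errors, but this is a logistic model, and step 3 shows that mean-dependent weights restore formal identification. Seven of the eleven literal fits returned estimates, and their treatment contrast was that of a sensible model. The divergences come from special-purpose code and assumed variances, and each simpler model also failed once.

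There is also a benign reading. The two levels named in the errors sentence match the two random intercepts in the sentence before it. If unstructured is the covariance type of those effects, each is a single variance and the model is A, which fits. This reading is available but strained: the text lists random effects and errors separately, and for a single intercept the word would specify nothing. It leaves two different models open rather than removing the problem.

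It is tempting as well to say that about five children per site cannot support an unstructured within-site matrix. That is not the right argument, since a common matrix would be pooled over about 60 sites. The sound objection is that no common matrix is defined.

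Finally, nothing in the documents says that a replacement would be chosen after unblinding. The protocol treats these analyses as optional, and multiple imputation, LOCF, tipping-point and per-protocol analyses also probe the primary result. That stands, and it limits the importance of the point.

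**Conclusion.** Wrong as written, for a sensitivity analysis only. Taken literally, the participant intercept and the visit matrix overlap almost completely, and the fit is likely to diverge or to set the participant variance to zero. In neither case is the model described the model fitted. The within-site part is undefined if it means residuals. Because a workable reading exists, the text is also ambiguous between models.

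The overlap and the undefined site matrix follow from the text alone. The frequency of failure (4 of 11, with the other 7 at or near the bound) rests on assumed variance components and non-SAS code and is only indicative. The claim that the model is impossible to fit does not hold. The primary logistic regression, the alpha control and the sample size do not change.

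**What to change.** Choose one structure and state it in SAP 7.2.4.1:

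- nested random intercepts for site and for participant within site, with no further residual covariance; or
- a site random intercept plus an unstructured within-participant matrix across Weeks 2, 4 and 8, with no participant intercept.

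The first keeps the random-effects sentence in both documents and needs only the errors sentence removed. The second drops the conditioning on the child, so its odds ratio is on a scale closer to that of the primary analysis.

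Under either choice, delete the within-site errors, name an estimation method that supports Kenward-Roger (for example restricted pseudo-likelihood), add the code as is done for the imputations, and name the other structure as the fallback for non-convergence.

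Protocol 10.4.1 carries the same specification. Either align it or record the departure in SAP 11.1, which now lists no changes to protocol-defined analyses. The cost is a few sentences and a code block, with no new data and no effect on the primary analysis, provided it is done before unblinding.

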7.2.4.2. Multiple Imputation

Multiple imputation with missing-at-random assumption will be used as an alternative method to handle missing data. A full conditional specification method (van Buuren 2007) that assumes the existence of a joint distribution for all variables will be used to impute the IGA score. A regression model including treatment group, stratification factor age group, and baseline and scheduled postbaseline IGA scores up to Week 8 will be specified for the fully conditional specification method. The imputation will be repeated 40 times to generate corresponding complete datasets in order to reflect the uncertainty around the true values. The primary endpoint binary response will be derived for each of the imputed datasets per the definition in Section 7.2.1.1 and the logistic regression described in Section 7.2.2 will be applied. The results will then be combined for the inference using Rubin's rule.

The following sample SAS code will be used for the MI:

```
proc mi data=mi_wide seed=18424305 n impute=40 out=impute_IGA;
  class trt01p agestrata;
  var trt01p agestrata avalBASELINE avalWEEK2 avalWEEK4  avalWEEK8;
  fcs REGPMM nbiter=30;
run;
```

7.2.4.3. Last Observation Carried Forward

For participants who are missing postbaseline values, the last observed nonmissing value will be used to fill in missing values at Week 8. The proposed logistic regression described in Section 7.2.2 will then be applied to the imputed dataset.

7.2.4.4. Tipping Point Analysis

A tipping point sensitivity analysis will be conducted to examine the potential effects of missing data. The missing binary IGA-TS response in each treatment group at Week 8 will be replaced by a range of values from the most conservative case to the most aggressive case. The most conservative case is that all the missing participants in active treatment groups are nonresponders and all the missing participants in the vehicle group are responders, while the most aggressive case is the other way around. For each scenario, between-treatment comparisons will be performed using a chi-square test. If there are N missing responses in the 1.5% BID arm and M missing responses in the vehicle arm, the following process will be used to determine the tipping point and a similar process will be implemented for the 0.75% BID arm versus the vehicle arm:

- Missing responses in the 1.5% BID arm will be imputed with a range of values from 0 to N.
- Missing responses in the vehicle arm will be imputed with a range of values from 0 to M.

- Treatment comparisons between the 1.5% BID arm and the vehicle arm will be analyzed in each of the $(N + 1) \times (M + 1)$ imputed datasets using a chi-square test, which will result in a $(N + 1) \times (M + 1)$ table; columns will represent the number of responses imputed for the 1.5% BID arm and rows will represent the number of responses imputed for the vehicle arm. A separate table will be generated to compare the 0.75% BID arm with the vehicle arm following the same process.

7.3. Analysis of the Key Secondary Efficacy Parameters

7.3.1. Key Secondary Efficacy Measures

7.3.1.1. Itch Numerical Rating Scale Score

The Itch NRS is a once-daily patient-reported measure of itch intensity assessed using an 11-point scale (0 = no itch to 10 = worst imaginable itch). Participants aged 6 years or older will be asked to record their highest (worst) level of itch in the evening over the 24-hour recall period.

The Itch NRS score for baseline will be determined by averaging the 7 daily NRS scores directly before Day 1 (Day -7 to Day -1) for all the by-visit summaries. The by-visit Itch NRS score for postbaseline visits will be determined by averaging the 7 daily NRS scores directly before the visit day. If 4 or more daily scores are missing (out of the 7), the Itch NRS score at the visit will be set to missing. For all daily itch related analyses, including time to achieve Itch NRS score improvement of at least 2 or 4 points analyses, baseline will be defined as the last available Itch NRS score during the week prior to Day 1 (Day -7 to Day -1).

The proportion of participants with a clinically relevant change in itch, defined as a ≥ 4 -point improvement in by-visit or daily Itch NRS score from baseline, will be summarized by treatment group for participants with baseline Itch NRS score ≥ 4 .

